12 WITHDRAWAL OF SUBJECTS

Participants will be given phone numbers for research associates and supervising physicians to call if there are adverse effects or other study-related problems. Participants will be advised that if they have any adverse effects and/ or wish to stop participating in the study for any reason, they are free to do so. Participants who are injured as a result of being in the study will have treatment available. The costs of such treatment may be covered by Roswell, depending on a number of factors.

Roswell Park Protocol No.: I 475819

Any participant who discontinues due to an AE must be followed until the event resolves or stabilizes. Appropriate medical care should be provided until signs and symptoms have abated, stabilized, or until abnormal laboratory findings have returned to acceptable or pre-study limits. The final status of AE will be reported in the participant's study records and to the study DSMB.

Reasons for intervention discontinuation/withdrawal from the study should be classified as follows:

- Death.
- Adverse side effects; related or unrelated to intervention.
- The Investigator may discontinue a participant if, in his/her judgement, it is in the best interest of the participant to do so.
- Noncompliance (defined as missing scheduled visit by more than 2 weeks without contact).
- Participant voluntary withdrawal. A participant may withdraw from the study at any time, for any reason.

13 RISKS TO SUBJECTS

The potential risks to participants in the clinical studies, and their likelihood and seriousness, are described below. Participants can choose, as an alternative, to not enroll in this study. Overall, there is minimal risk for serious adverse reactions as a consequence of enrolling in this study.

- *Nicotine overdose:* Some people who use ENDS may experience symptoms of nicotine overdose such as nausea, sleep disturbance, headache, and vomiting; however, these symptoms are usually mild and temporary. Before ENDS are used in human participants, they have undergone laboratory testing to assess the yields of nicotine present in the products; this will also provide quality control information to select the safest product.
 - The PK studies using ENDS in participants will be performed in a clinical setting accustomed to monitoring for adverse effects. The PI and Co-I's have considerable experience with conducting outpatient studies on novel nicotine delivery devices and their effects on participants, and will be able to provide appropriate safety monitoring.
 - Participants will also be instructed that the investigational products are not to be ingested. If a product is ingested by mistake, the participant will be instructed to call the study physician ([name]). If they are experiencing serious symptoms of nicotine overdose, the participant should contact Poison Control or Emergency Medical Services.
- *Nicotine withdrawal:* Many individuals who quit smoking exhibit a pattern of symptoms related to withdrawal from tobacco use. These symptoms include: sadness and anxiety, irritability, anger, difficulty concentrating, appetite change and weight gain, insomnia, and decreased heart rate. Because participants in the studies will be asked to refrain from smoking and or using their ENDS for portions of the study, it is likely that they will experience some of these symptoms. Consent forms will include sections describing the possibility of this occurrence. Study personnel will be trained to recognize these symptoms and educate the participants about them.
- *Respiratory irritation:* Some people who use ENDS may experience irritation of the mucosal membranes of the upper respiratory tract, but as they are already regular ENDS

Roswell Park Protocol No.: I 475819

users we do not think that this is likely. We will exclude participants or postpone procedures if they demonstrate chronic or acute respiratory problems.

- *Inconvenience*: It is quite probable that participants will experience *inconvenience* due to the multiple study visits required.
- *Venipuncture* is required for study participation and this could lead to local pain, swelling, bruising or infection. Significant complications (beyond typical local pain and mild bruising) are expected to be uncommon. *The volume of blood to be withdrawn will never exceed 60 mL on any planned visit*. This amount of blood is safe for the participants and will not produce any injury to a healthy individual.
- *Emotional distress*: Participants may experience psychological discomfort during assessments when discussing feelings and attitudes about smoking and using ENDS, or from learning about the risks of smoking. However, all participants will be current ENDS users and we do not expect this type of reaction to be likely. Study personnel will be alerted to expect this from a small number of participants and will be trained to make referrals for mental health services as needed. Personnel will be trained to query for adverse emotional reactions during assessments and will be trained to deal with such reactions and to provide additional referrals if needed. In addition, if assessments indicate psychiatric concerns, referrals to appropriate psychological services will be provided.
- *Reproductive Risks*: Women will be advised to notify the study staff if they become or intend to become pregnant during the study period. Because nicotine and e-cigarette vapor safety for an unborn baby is unknown, participants will be told that they should not become pregnant while on this study nor should they nurse a baby. If a woman is pregnant or breast feeding, she may not participate in this study, and if she becomes pregnant during the study, she will be removed from the study.

As general measures to minimize the likelihood of participants experiencing these side effects staff will have the study physician's ([name]) cell phone number and will contact [name] with all questions and concerns. We will also:

1. Employ a stringent list of exclusionary criteria to limit the chance of side effects listed above occurring. Potential participants will be screened for medical illnesses that would preclude the ENDS use and/or increase the risk of adverse events or side effects (e.g., respiratory diseases, cardiovascular conditions).
2. Administer the ENDS of the highest quality (based on the outcome of the pre-clinical studies).
3. Monitor self-reported side effects at each assessment time-point (i.e., each clinic visit). Participants will be informed about the potential for adverse events or side effects from ENDS use, including upper respiratory tract mucosa irritation, cough, phlegm, headache, nausea, and emotional distress from learning about the adverse health consequences of smoking. Participants will be told that they should proceed with caution until they are certain that ENDS do not affect their performance.
4. The study physician ([name]) will be alerted to any severe side effects or any reported adverse events. The study physician will review the information provided by the research staff and if applicable, will contact the study participant within 24 hours after being notified

Roswell Park Protocol No.: I 475819

to gather more information and determine the appropriate course of action for the participant. Ultimately, the study physician will decide if the adverse event is related to study treatment and whether the participant should discontinue its use.

Participants will be told that they should proceed with caution when using ENDS and to report any adverse symptoms or side effects to study personnel immediately.

14 POTENTIAL BENEFITS TO SUBJECTS

There is no direct benefit for those who decide to participate and enroll in this study.

15 DATA AND SPECIMEN BANKING

Pharmacokinetic Blood Sample Collection

Whole blood samples for analytical testing of nicotine and cotinine levels will be collected via venipuncture using a butterfly needle or a venous catheter using 4 mL green-top heparinized collection tubes. The blood will be drawn by either a certified study phlebotomist using a butterfly needle, or a venous catheter placed by a registered nurse. Blood sample collection will be obtained at each study visit prior to and 2, 4, 5, 6, 8, 10, 13, 15, 20, 30, 45, 60, 90, and 120 min after onset of use of each nicotine solution, approximately 4 mL will be taken at each time point (not all collection time points will be fulfilled at each study visit). If the participant is experiencing excessive blood clotting, the butterfly needle will be removed and a new butterfly needle will be inserted to continue with blood collection (the number of new butterfly needle insertions will never exceed three per study visit). The butterfly needle or venous catheter may be placed in the upper extremity or in the hand of the participant.

For all participants, the amounts drawn will not exceed 240 mL for the entire study and collection will not occur more frequently than 2 times per week.

Urine Sample Collection

Urine samples will be taken before and after ENDS product use. Female urine samples will be tested for pregnancy.

All blood and urine samples will be immediately transported to the Health Behavior Department Laboratory (Roswell Park Comprehensive Cancer Center); the blood samples will be centrifuged to separate the plasma from whole blood. The plasma will be aliquoted into cryovials that are labeled with the participant's initials, participant's study number, clinical study number, protocol time point, product, and protocol day. Urine samples will be transferred to 15 mL Flacon tubes. The samples will immediately be frozen at -70°C or below in [name] until analyzed. Plasma will be analyzed for cotinine and nicotine using UPLC-MS/MS method (6). Urine samples will be tested for cotinine, NNAL and VOC metabolites. Female urine samples will be tested for pregnancy. All blood and urine sample results are recorded in logs and kept in:

[name]
Gratwick Basic Science Building (GBSB)
Health Behavior Department Laboratory
Laboratory location: 4th Floor, Room 4942
Laboratory [contact]
[name] office number: [contact]

Roswell Park Protocol No.: I 475819

If there are remaining blood or urine samples after all analysis has been done and the participant checks yes on the consent document to having any extra samples stored for future studies, then the samples will be kept in a -70°C or below freezer in [name] Laboratory listed above. If there are remaining samples and the participant checks no on the consent document to having any extra samples stored, then the extra samples of that participant will be immediately destroyed once they are taken off study or completed.

Any future research on the remaining samples will only be done under IRB-approved protocols.

Note: All investigator or analyzing research laboratories housing research samples need to maintain current Temperature Logs and study-specific Sample Tracking and Shipping Logs. The Principal Investigator/Laboratory Manager must ensure that the stated lab(s) have a process in place to document the receipt/processing/storage/shipping of study-related samples/specimens. This is required for both observational and interventional clinical studies collecting clinical samples.

16 MEASUREMENT OF EFFECT

Not Applicable

17 SAFETY EVALUATION

17.1 Safety Monitoring

ENDS have been used before by us or by other researchers that we are aware of, and the risks appear to be minimal. Monitoring for safety will be carried out by review of all clinical complications and all of the data by the PI and Co-Investigators including Physicians. Reporting of adverse events will follow requirements mandated by the both IRBs (Committees on Human Research, CHRs). This will be followed by a detailed written report within ten (10) working days. In addition, any incidents or problems involving the conduct of the study or patient participation, including problems with the recruitment and/or consent processes will be reported within ten (10) working days. The Principal Investigator will provide a discussion of any problems noticed during each year in the course of the study to the both IRBs (CHRs) on an annual basis. The standard adverse event grading scale will be used to report any potential adverse events from phlebotomy, study device or other study procedures: 1) Mild AE – did not require treatment; 2) Moderate AE – resolved with treatment; 3) Severe AE – resulted in inability to carry on normal activities and required professional medical attention; 4) Life-threatening or disabling AE; and 5) Fatal AE. The supervising study physician will be notified of all grades 2 through 5 AEs. Additionally, [name] will be notified of all grades 4 and 5 AEs. Grade 3 through 5 AEs will be reported to the IRBs (Grades 4 and 5 - within 24 hours; Grade 3 - within 10 days). Grade 2 will be included in the yearly progress report. Grade 1 will not be reported. Frequency of Safety Reviews: Subject safety data reporting is a formal part of weekly research group meetings at both collaboration centers and during teleconferences between PI and Co-I; safety reviews will be conducted through review of all clinical complications and data when it returns, including laboratory data. Safety data are collected on a daily basis. Safety reviews will be conducted annually in conjunction with the protocol renewal to IRBs.

Roswell Park Protocol No.: I 475819

17.2 Unanticipated Problems

An Unanticipated Problem (UP) is any incident, experience, or outcome that meets all of the following criteria:

- Unexpected (in terms of nature, severity, or frequency) given:
 - The research procedures that are described in the study-related documents, including study deviations, as well as issues related to compromise of participant privacy or confidentiality of data.
 - The characteristics of the participant population being studied.
- Related or possibly related to participation in the research (possibly related means there is a reasonable possibility that the incident, experience, or outcome may have been caused by the procedures involved in the research).
- Suggests that the research places participants or others at a greater risk of harm (including physical, psychological, economic, or social harm) than was previously known or recognized and if in relation to an AE is also deemed Serious per Section 17.7.

17.2.1 Reporting Unanticipated Problems

The Reportable New Information (RNI) Form will be submitted to the CRS Quality Assurance (QA) Office within 1 business day of becoming aware of the Unanticipated Problem. After review, CRS QA Office will submit the RNI to the IRB.

When becoming aware of new information about an Unanticipated Problem, submit the updated information to CRS QA Office with an updated Reportable New Information Form. The site Investigator or designated research personnel will report all unanticipated problems to the IRB in accordance with their local institutional guidelines.

18 DATA MANAGEMENT AND CONFIDENTIALITY

To ensure data security and confidentiality, all assessments will be administered by trained research study staff, and blood draws will be performed by certified phlebotomists or registered nurses.

Data management activities will be performed using REDCap (Research Electronic Data Capture). REDCap is a secure web-based application that supports data capture and management for research studies. In the event of REDCap being inaccessible for a study visit, paper copies of the questionnaires will be administered to the participant at that point in time and data entry will be performed by the assigned Senior Research Associate after the study session is completed. Data can be entered and changed only by those with the rights to do so.

All participant records and data will be held in the Health Behavior Department at Roswell Park Comprehensive Cancer Center. All personnel involved in the conduct of this study are Roswell Park staff.

- Access to the data by all necessary research personnel will be through a password-protected network computer. At no time will data be downloaded on a thumb drive or other portable media or laptop. Participant identity will not be disclosed in the event of publication or sharing of data.

Roswell Park Protocol No.: I 475819

- Participant identity will not be disclosed in the event of publication or sharing of data.
- Any paper files containing identifiers (if applicable to the research) will not be taken off Roswell Park premises; they will be kept in a locked filing cabinet in a secure building on the Roswell Park's campus.
- PHI will not be re-used or disclosed for purposes other than research use.
- There are no outside entities to which PHI will be disclosed.
- Essential documents will be retained per Roswell Park's policy for 6 years from the study termination date. These documents could be retained for a longer period, however, if required by the applicable local regulatory requirements or by an agreement with Roswell Park.

19 STATISTICAL PLAN

19.1 Sample Size Determination

The sample size calculations are based on the primary analysis of the area under plasma nicotine concentration-time curve (AUC nicotine), which is compared between salt and free-base forms of e-liquid. A simplified calculation is based on the two-sided two-sample t-test, where a sample size of n=18 provides 80% power (at a significance level of 0.05) to detect a true difference of at least 700 ng/mL × min. This is based on the assumption that the within-patient standard deviation of the response variable is 500 ng/mL × min.

The reduction in AUC of 700 ng/mL × min corresponds to 4-fold reduction in nicotine content in tobacco cigarettes. This effect was observed among smokers who switched from cigarettes with high nicotine content (12 mg) to low nicotine content cigarettes (4 mg)

To account for potential drop-out, a maximum of 20 participants will be enrolled. Accrual for this study is expected to take 4 years.

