9 DESIGN

This is a single center, randomized, double blind clinical trial pilot. Using a 2 (free-base vs salt) x 2 (tobacco vs unflavored) factorial design, 20 current daily vapers will be asked to use one of four liquids across four 2.5-hour laboratory sessions. The order of the tested conditions will be randomized and study personnel as well as participants will be blinded to the four liquids throughout the study. Participants will be aged 21-55, use a vaping product daily, have a preferred flavor of tobacco, and not currently smoke cigarettes (no cigarette use in the past seven days and no more than 5 cigarettes in last 30 days). For each session, participants will arrive after overnight abstinence and be randomly assigned to one of the four liquids and puff according to a standardized protocol (10-minute bout, 20 puffs, 30 second inter-puff interval). Venous blood samples (4 mL) to measure nicotine will be drawn by a either certified phlebotomist through a butterfly needle or

Roswell Park Protocol No.: I 475819

through a catheter by a certified registered nurse before and at 2, 4, 5, 6, 8, 10, 13, 15, 20, 30, 45, 60, 90, and 120 min after onset of use. Samples will be processed within 2 hours and frozen at -80°C until analysis. Plasma samples will be analyzed for nicotine concentration using sensitive and validated UPLC-MS/MS method developed by TCORS analytical core located at Roswell Park. At the same time intervals, participants will complete standard subjective effects measures, including the Drug Effects scale, ENDS Nicotine Dependence Scale, Minnesota Nicotine Withdrawal Scale, Product Evaluation Scale, and the Duke Sensory questionnaire, Delay Discounting Task and the ETM with the product being tested available for the fixed price in the marketplace. Participants will be compensated by cash for each study visit completed and will receive an additional \$90.00 bonus if all study visits have been completed (**Table 1**).

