10.1 Dosing and Administration

The device will be filled with either (1) free-based nicotine e-liquid solution of unflavored (2) free-based nicotine e-liquid solution of tobacco flavor (3) salt-based nicotine e-liquid solution of unflavored or (4) salt-based nicotine e-liquid solution of tobacco flavor. Both the study personnel and study participants will be blinded to the solution flavor and nicotine concentration. All e-liquids will contain 0.148M nicotine (24 mg/mL free-base nicotine or 24 mg/mL nicotine benzoate). Participants are randomized to the order of the e-liquids by the study statistician using the Williams Design; a special case orthogonal latin squares design generated using SAS v9.3.

Intervention will be administered on an outpatient basis. Reported adverse events (AEs) and potential risks are described in **Section 13** and **Section 17**.

Nicotine (3-(1-methylpyrrolidin-2-yl)-pyridine) the primary alkaloid in tobacco products binds stereo-selectively to nicotinic-cholinergic receptors on autonomic ganglia, the adrenal medulla, neuromuscular junctions and in the brain. Nicotine exerts two effects, a stimulant effect exerted at the locus ceruleus and a reward effect in the limbic system. Intravenous administration of nicotine causes release of acetylcholine, norepinephrine, dopamine, serotonin, vasopressin, beta-endorphin and ACTH. Nicotine is a highly addictive substance. Nicotine also induces peripheral vasoconstriction, tachycardia and elevated blood pressure. Nicotine replacement therapies (like inhalers and patches) are used to treat smoking withdrawal syndrome. Nicotine is classified as a stimulant of autonomic ganglia.

Electronic nicotine delivery systems (ENDS) usually look similar to regular cigarettes, cigars, pipes, or pens, but do not contain tobacco. Instead, they are comprised of a battery-powered atomizer that produces vapor for inhalation from solutions that contain nicotine. Electronic cigarettes (e-cigarettes) are the most popular ENDS on the market. Different ENDS brands are engineered differently. The differences include the appearance, the nature of nicotine solution, the capacity of the cartridge containing the solution, the nature of the heating element, and size and

Roswell Park Protocol No.: I 475819

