19.2 Randomization

This study is a randomized within-subject cross-over study, where the order of *four types of nicotine solutions* that the participant receives will be randomized. Participants will be provided with cartridges of maximum available amounts of nicotine (labeled as high: approx. 24 mg). All participants and study personnel will be blinded to the flavor names and nicotine content in cartridges. Participants will be provided with cartridges of different nicotine solutions at each visit, instructed on how to use the product, and partake in the controlled 10-minute puffing session (1 puff every 30 seconds, 20 puffs total).

Note: In order to minimize any carry-over effect, there will be a minimum 5-7-day wash-out period between each scheduled study visit and, the order of the nicotine solutions will be randomly assigned (with a different randomization order for each participant). In addition, we will consider linear mixed models that will incorporate a carry-over effect. This will provide a more conclusive analysis, but also potentially validate the effectiveness of the wash-out period, which could help in the design of future studies.

Roswell Park Protocol No.: I 475819

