19.4 Primary Analysis

The primary objective is to evaluate whether AUC nicotine, C_{max} or T_{max} differ between free-base and salt-based versions of the same liquid, controlling for flavoring and nominal nicotine concentration.

Each outcome will be modeled as a function of base (free-base versus salt-based), flavor (tobacco versus unflavored), their interaction, prior combination indicator (for carry-over effect), and a random subject effect using a linear mixed model. All model assumptions will be verified graphically and transformations will be applied as appropriate. The effect of “base” on the AUC nicotine, C_{max} and T_{max} measures will be evaluated using tests about the least square means of “base”. Additionally, 95% confidence intervals about the mean differences will be obtained.

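### Section 4's target of 20 completers cannot survive one drop-out under the cap of 20 enrolled, and Section 19.1's 80% power is that of 9 versus 9 independent participants, not of the planned crossover

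*Combined protocol and SAP*

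**What the plan says.** **Number of participants.** Section 4 sets the accrual target at 20 evaluable participants and defines evaluable as having completed all four visits. Section 11 recruits 20 in total. Section 19.1 calculates 18 and enrols at most 20 so as to absorb drop-out. No drop-out rate is given.

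**Power.** Section 19.1 powers the comparison of AUC between salt and free-base liquids: "A simplified calculation is based on the two-sided two-sample t-test, where a sample size of n=18 provides 80% power" at a significance level of 0.05 for a difference of 700 ng/mL × min. On the SD it says: "This is based on the assumption that the within-patient standard deviation of the response variable is 500" (ng/mL × min). It gives no source for that value. The 700 is justified only by a 4-fold reduction in cigarette nicotine content, illustrated by a switch from 12 mg to 4 mg.

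**Design and analysis.** Section 9: "20 current daily vapers will be asked to use one of four liquids across four 2.5-hour laboratory sessions". Section 19.2: "This study is a randomized within-subject cross-over study". Section 10.1: "Participants are randomized to the order of the e-liquids by the study statistician using the Williams Design". The Section 19.4 model contains base, flavor, their interaction, a "prior combination indicator (for carry-over effect), and a random subject effect using a linear mixed model". No power is stated for that model.

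**The concern.** Two statements about sample size do not match the rest of the plan.

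First, 20 completers from at most 20 enrolled requires that nobody drops out, yet Section 19.1 offers 20 as the number that already allows for drop-out. A reader cannot tell whether the evaluable target is 18 or 20.

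Second, a two-sample t-test compares independent groups, and this trial has none. Each participant has two salt and two free-base sessions, and the SD supplied is described as within-patient. The stated power and difference are therefore not those of the planned analysis. At stake is an accurate account of what the trial can detect on AUC. That account matters to anyone planning a later study from this pilot.

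**Working it through.** **Inputs from Section 19.1:** difference 700, SD 500, two-sided alpha 0.05, n = 18, power 80%. All power figures use the noncentral t distribution. AUC is in ng/mL × min.

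1. **Reproducing the plan's figure.** For two independent groups of m, SE = 500 × √(2/m), with 2m − 2 df.
   - m = 9: SE = 235.7, 700/235.7 = 2.97, df 16, power 79.6%.
   - m = 18: power 98.3%.

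   The 80% is therefore a total of 18 split 9 and 9. The split is inferred, since the text does not state it.

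2. **Same inputs in the crossover, constant salt effect.** Take 500 as the residual SD of one session. The base effect per participant is the mean of two salt sessions minus the mean of two free-base sessions, with variance 500²/2 + 500²/2 = 500². Without carry-over, SE = 500/√18 = 117.9, with 51 df.
   - Power at 700: 99.99%.
   - Difference with 80% power: 2.856 × 117.9 = 337.

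3. **With the carry-over term.** SE = 500 × √(v/18), where v comes from the design matrix. Subject is treated as fixed, which gives an upper bound on the SE of the random-subject model; df 47. The layout is five disjoint Williams squares, that is, 20 distinct orders. This satisfies Section 10.1 and also the Section 19.2 remark "with a different randomization order for each participant". Losing any two of the 20 gives v = 1.059 to 1.177.
   - SE: 121.3 to 127.9.
   - Difference with 80% power: 2.860 × SE = 347 to 366.
   - Power at 700: at least 99.97%.

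4. **If the salt effect differs between participants.** Let its between-participant SD be τ. The documents give no value, so this is an assumption. Without carry-over, SE = √((τ² + 500²)/18), df 17, and the 80%-power difference is 2.973 × SE.

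| τ | SE | 80%-power difference | Power at 700 |
|---|---|---|---|
| 250 | 131.8 | 392 | 99.9% |
| 500 | 166.7 | 495 | 97.7% |
| 750 | 212.5 | 632 | 87.4% |
| 865 | 235.5 | 700 | 80.0% |

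   The shortcut stops being conservative near τ = 865.

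5. **Drop-out.** 20 enrolled − 1 = 19, below Section 4's 20. Against 18, the cap allows 20 − 18 = 2 losses (10%). For illustration, with independent drop-out at assumed rates d of 2%, 5% and 10%, the chance that all 20 complete is (1 − d)²⁰ = 67%, 36% and 12%. The binomial chance that at least 18 complete is 99%, 92% and 68%.

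6. **Justification of 700.** 12 mg / 4 mg = 3, not 4.

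**The case against.** The strongest reply is that Section 19.1 calls its calculation simplified, names the test and gives a figure that reproduces. It does not claim that 700 is the smallest difference the mixed model can detect, and a disclosed conservative shortcut is common practice. That stands against any charge of an arithmetic error. It does not tell the reader that n = 18 means 9 per group, that the result is meant as a bound, or where 500 comes from.

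On numbers, Section 4's 20 is a target, no analysis is restricted to completers, and the mixed model can use participants with missing visits. That also stands, and it makes the conflict editorial. The three sections still cannot all be met after one loss.

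A reader might infer more than the documents support:

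- **That the trial is underpowered.** For AUC at 700, the same inputs point the other way.
- **That the trial can always detect about half of 700.** That needs 500 to be the one-session residual SD and the salt effect to vary little between participants.
- **That the shortcut is conservative for every endpoint.** The documents give no SD or effect size for C_max, T_max or the flavor-by-base interaction on subjective effects, so nothing is shown for them.
- **That the carry-over term is in doubt.** Section 19.2 says "we will consider linear mixed models that will incorporate a carry-over effect", but Section 19.4 already lists the term. Including it moves the detectable difference only from 337 to 347–366.

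**Conclusion.** The point holds as a minor one, in three parts.

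- **Evaluable number.** Sections 4, 11 and 19.1 conflict. This needs no assumption: one drop-out leaves at most 19 completers.
- **Power statement.** The 80% describes a 9-versus-9 parallel comparison. For the AUC main effect of base with 18 completers, power at 700 exceeds 99.9% if 500 is the one-session residual SD and the salt effect is constant. It is lower if the effect varies between participants, and reaches 80% only near a between-participant SD of 865. The shortcut is thus a conservative bound for AUC under those conditions, and only there.
- **Justification of 700.** The stated fold-change does not match its own example.

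The AUC target is not shown to be at risk, and the 95% confidence intervals in Section 19.4 remain the basis for reading the result.

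**What to change.** 1. State one evaluable target in Sections 4, 11 and 19.1, for example 18 evaluable of at most 20 enrolled. If the two-sample calculation is replaced, justify 18 from the new one, because 18 now rests on the shortcut alone.
2. Say what the SD of 500 refers to and give its source.
3. Restate power and detectable difference for the base main effect under the Section 19.4 model and the sequences actually generated, with the assumption made about between-participant variation in the salt effect. Alternatively, keep the shortcut and say that n = 18 means 9 per group and that it is a conservative bound for AUC under stated assumptions. The figures above are checks, not text for the protocol.
4. Reconcile the 4-fold statement with 12 mg to 4 mg, since it is the only support given for 700.

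The cost is wording in Sections 4, 11 and 19.1 and, if the calculation is replaced, one short recalculation by the study statistician. Enrolment need not change.
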